The Effect of Intravenous Infusion of Tramadol-ondansetron on Recovery After Caesarean Section (TRON)

NCT05879536

Statistical Analysis Plan

Protocol Number: TRON

Version: 1.5

Date: 20/08/2024

Introduction

This Statistical Analysis Plan (SAP) outlines the statistical methods and procedures to be used for analyzing data from the study evaluating the non-inferiority of intravenous tramadol-ondansetron (TRON) compared to epidural analgesia (AL-EPI) in post-cesarean recovery.

Study Objectives

Primary Objective

- Evaluate the non-inferiority of TRON compared to AL-EPI in terms of global post-cesarean recovery.

Secondary Objectives

- Assess non-inferiority of TRON versus AL-EPI in acute post-cesarean pain control.
- Compare the incidence of adverse effects between TRON and AL-EPI.
- Evaluate the non-inferiority Of TRON compared to AL-EPI in the obstetric quality of recovery.
- Evaluate the incidence of chronic post-cesarean pain between TRON and AL-EPI.

Study Design

Prospective observational cohort study

Study Population

Inclusion Criteria:

- Patients over 18 years old undergoing cesarean section receiving any of the analgesic strategies studied.
- Consent to participate in the study.

Exclusion Criteria:

- Receiving an analgesic medication other than the one mentioned as "routine multimodal analgesia" (either as regular medication or for acute post-surgical pain)
- Medical history that determines the baseline data of the scales and data that we collect (pain or previous disabilities; addiction to drugs, alcohol or drugs; another disease that worsens the quality of life)
- Medical history that conditions the pharmacological effect (allergy, intolerance or atypical reaction to any of the drugs involved in its treatment or possible cross-reactions)
- Contraindication for neuraxial techniques (patient refusal, difficulty in understanding or communication, localized infection, increased intracranial pressure, or other medical criteria)
- Two or more previous caesarean sections
- Difficulty in understanding or communication
- Mother care will not be available to the newborn in the postpartum period for any reason

Endpoints

Primary

Recovery quality measured by the QoR-15 scale at 24 and 48 hours post-cesarean.

Secondary

- Pain levels measured by the Visual Analog Scale (VAS) every 4 hours for 48 hours.
- Adverse effects within 48 hours post-cesarean.
- Obstetric quality of recovery measured by the Obstetric Quality of Recovery-10 (ObsQoR-10).

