- Incidence of chronic pain at 90 days post-cesarean measured by the Numerical Rating Scale (NRS).

Randomization and Blinding

This study does not involve randomization as it is observational. Blinding is not applicable.

Sample Size and Power Calculations

The minimum clinically important difference (MCID) of QoR-15 is 8 points, so we used it as the equivalence threshold. [Anesthesiology 2016 Jul;125(1):39-45]. We used data from previous analgesia studies using this tool with an expected mean of 120 points

with a standard deviation of 28.4. [Anesthesiology 2018; 128:598-608]. Therefore, we calculated that 312 patients are needed to conduct this non-inferiority study of tramadol-ondansetron perfusion with an alpha error of 0.05 and a statistical power of 0.8.

Data Collection and Management

Patient data will be collected at baseline, 24 hours, 48 hours, and 90 days post-cesarean. Data will be extracted from the hospital electronic health records.

Statistical Methods

A statistical analysis of the results obtained from the Quality of Recovery (QoR) 15 questionnaire will be conducted. The sequential Visual analog scale (VAS) pain scores, adverse effects, and the need for rescue medication will be analyzed. Additionally, the Obstetric Quality of Recovery-10 (ObsQoR-10) results will be analyzed to validate the Spanish-translated version and define the minimal clinically significant difference (MCID). Finally, the incidence of chronic postoperative pain will be studied by analyzing NRS results and medication use. A p-value of <0.05 is considered significant.

1. **QoR-15:** A mixed linear regression model will be fitted introducing the type of analgesia (TRON vs EPI) and the covariables considered in the model as fixed effects, with the patient as a random effect. The following covariables will be introduced in the model:
 - Weight of the newborn: quantitative variable in Kilograms
 - Breastfeeding: Yes or no
 - Duration of intervention: quantitative variable in minutes.
 - Previous caesarean section: Yes or no
 - Elective, urgent or emergency caesarean section.
 - Extended surgery: tubal sterilization or any other deviation from a standard caesarean section.
2. **Sequential VAS:** Scale from 0-10 repeated every 4 hours. It will also employ a mixed linear regression model, introducing the same covariables as mentioned in the previous section.

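### The primary objective is non-inferiority on QoR-15, but the only decision criterion is p<0.05: the 8-point margin, sidedness, confidence interval and deciding time point are absent from the analysis.

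*SAP*

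**What the plan says.** - **Primary objective** (Study Objectives): "Evaluate the non-inferiority of TRON compared to AL-EPI in terms of global post-cesarean recovery".
- **Primary endpoint** (Endpoints): "Recovery quality measured by the QoR-15 scale at 24 and 48 hours post-cesarean". Neither time is named as the deciding one.
- **Margin** (Sample Size and Power Calculations): "The minimum clinically important difference (MCID) of QoR-15 is 8 points, so we used it as the equivalence threshold". The 8 points appear nowhere else.
- **Sample size** (same section): "312 patients are needed to conduct this non-inferiority study of tramadol-ondansetron perfusion with an alpha error of 0.05", with power 0.8, expected mean 120 and SD 28.4. Sidedness and group ratio are not given.
- **Decision criterion** (Statistical Methods, opening paragraph): "A p-value of <0.05 is considered significant". This one sentence covers every outcome, including those where the aim is a plain comparison, such as adverse effects.
- **Primary model** (Statistical Methods, item 1): a linear mixed model with analgesia type and six covariables as fixed effects and patient as random effect. Neither time nor an analgesia-by-time interaction is listed.
- **Secondary objectives**: non-inferiority is also sought for pain ("Assess non-inferiority of TRON versus AL-EPI in acute post-cesarean pain control") and for ObsQoR-10. This document gives no margin for either, and Statistical Methods plans to derive an ObsQoR-10 MCID from the study's own data.

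**The concern.** A non-inferiority conclusion needs a null hypothesis placed at the margin, or equivalently a confidence limit compared with it. The analysis section gives neither. By default, the p-value for the analgesia coefficient tests a difference of zero. A significant result says the groups differ, not whether the deficit is smaller than 8 points. A non-significant result says only that no difference was detected.

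Two things are at stake. First, a reader could take non-significance as non-inferiority, with an error rate well above the planned 5%. Second, the sidedness, the confidence level and the deciding time point remain unwritten and could be settled after the data are seen. Calling the margin an equivalence threshold in a non-inferiority study adds to the uncertainty.

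**Working it through.** **Inputs from the SAP:** margin 8, SD 28.4, alpha 0.05, power 0.8, total 312.

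**Assumptions, not in the SAP:** true difference 0 for power, 312 analysed with no dropout, no precision gained from covariates, 1:1 groups (2:1 as a variant), and a 24/48 h correlation of 0.3 to 0.7.

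**1. Reproduce 312.** n per group = 2 × (SD × (z₁₋α + z₀.₈) / margin)².
- One-sided 0.05: 2 × (28.4 × (1.645 + 0.842) / 8)² = 155.8, so 156 per group and **312** in total. Exact match.
- One-sided 0.025: 197.8, so 198 per group and 396 in total. No match.
- Equivalence (two one-sided tests at 0.05, same power): 216 per group, 432 in total. No match.

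The sample size is therefore sound, and it implies one-sided 0.05, that is, a two-sided 90% CI.

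**2. Standard error of the group difference.**
- One time point, 1:1: 28.4 × √(2/156) = 3.216.
- 24/48 h average, correlation r: 3.216 × √((1 + r)/2). At r = 0.5 this is 3.216 × √0.75 = 2.785.
- One time point, 2:1 (208/104): 28.4 × √(1/208 + 1/104) = 3.411.

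**3. Error if non-significance is read as non-inferiority, true difference -8.** P(two-sided p ≥ 0.05) ≈ Φ(1.96 − 8/SE). The ambiguous band holds observed differences that are not significant yet fail the 90% CI rule; it runs from −1.96 × SE to −8 + 1.645 × SE.

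| Setting | SE | Error | Ambiguous band (points) |
|---|---|---|---|
| One time point, 1:1 | 3.216 | Φ(−0.528) = 0.299 | −6.3 to −2.7 |
| Average, r = 0.5, 1:1 | 2.785 | Φ(−0.913) = 0.181 | −5.5 to −3.4 |
| One time point, 2:1 | 3.411 | Φ(−0.385) = 0.350 | −6.7 to −2.4 |

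For the average, the error is 0.130 at r = 0.3 and 0.230 at r = 0.7.

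**4. What the unstated choices do at 312, 1:1.** For a single contrast, power at true difference 0 is Φ(8/SE − z).

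| Rule | Result |
|---|---|
| One time point, 90% CI | Φ(2.488 − 1.645): power 80% |
| One time point, 95% CI | Φ(2.488 − 1.960): power 70%; 396 patients needed for 80% |
| Average, 90% CI | power 92.5% / 89.0% / 85.4% (r = 0.3 / 0.5 / 0.7) |
| Both time points required, 90% CI (bivariate normal) | power 66.7% / 68.8% / 71.3% |
| Either time point suffices, 90% CI (bivariate normal) | type I error at -8: 9.3% / 8.8% / 8.0% |

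**The case against.** The strongest reply is that the test can be recovered. The objective is non-inferiority, the SAP gives a margin and an alpha, and of the designs tried only one-sided 0.05 gives 312. A different margin or alpha would contradict the stated sample-size basis. Likewise, a single analgesia term with a patient random effect suggests one contrast pooled over 24 and 48 hours, and with complete data the omission of time does not bias that contrast.

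This has weight for the margin, and it makes the pooled figure of about 18% a better match to the listed model than 30%. It does not close the gap. Sidedness emerges only by back-calculation, the one rule that is written tests something else, and the SAP never says that the pooled contrast decides.

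Other reservations are fair:
- The 30% and 18% arise only if someone misreads non-significance. The SAP does not endorse that reading, but does not exclude it.
- The both and either rules and the 2:1 ratio are illustrations, not SAP proposals.
- In a non-randomised cohort, adjustment can inflate the standard error. Variance inflation of 1.1 to 1.3 would lower the single-time-point 80% to about 77% to 70%, so the power figures may be optimistic.
- Margins for VAS and ObsQoR-10 may be in the protocol, which is not at hand. That part is secondary.

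**Conclusion.** The concern holds and must be fixed before analysis. The model can supply the required estimate and 312 is correctly calculated, but the written criterion does not turn that estimate into an answer to the primary question. This is a stated rule that does not match the objective, not merely missing detail.

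If the rule were misread, the error at a true 8-point deficit would be about 18% for the pooled contrast (13% to 23% over the assumed correlations) and about 30% for one time point, against 5% planned. The open choices alone move power from about 67% to 93%, and could raise the type I error to 8% to 9%. All these figures rest on SD 28.4, 312 analysed, 1:1 groups, no dropout and no effect of covariate adjustment on precision.

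**What to change.** For the primary objective, replace the general criterion with:

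> TRON is non-inferior if the lower limit of the two-sided 90% CI (one-sided alpha 0.05) for the adjusted TRON minus AL-EPI mean difference in QoR-15 lies above -8 points. A non-significant p-value is not evidence of non-inferiority.

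Also:
- State before analysis whether 24 h, 48 h, both or their average must meet the rule, and put time in the model accordingly. A workable default is the average, which fits the single analgesia term now listed, with a time term added and the 24 h and 48 h differences (from an analgesia-by-time term) reported with CIs.
- If a 95% CI is preferred, restate power at 312 as about 70% for one time point.
- Call the 8 points a non-inferiority margin.
- For VAS and ObsQoR-10, either fix margins before analysis from sources outside this dataset, or report differences with CIs and make no non-inferiority claim. An ObsQoR-10 MCID derived in this study should not serve as the margin in the same data.

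**Cost:** SAP wording only, no new data. Some secondary non-inferiority claims may become plain estimates. An average can hide a difference at one time point. A 95% CI applied to one time point, or a rule requiring both time points, brings power below 80% at 312.

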3. **ObsQoR-10:** A mixed linear regression model will be fitted introducing the same covariables as mentioned in the previous section.
4. **Adverse Effects:** Count of events as yes/no. A mixed Poisson regression model introducing the same covariables as mentioned in the previous section.

5. **Rescue Medication:** Count of events as yes/no. A mixed Poisson regression model introducing the same covariables as mentioned in the previous section
6. **Chronic Pain at 90 Days:** A Mixed logistic regression model introducing the same covariables as mentioned in the previous section.

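### The QoR-15 model lists no time term although the primary endpoint has two times, and the contrast held against the 8-point margin is not named

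*SAP*

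**What the plan says.** Under Study Objectives, the primary objective is: "Evaluate the non-inferiority of TRON compared to AL-EPI in terms of global post-cesarean recovery". The primary endpoint, under Endpoints, is: "Recovery quality measured by the QoR-15 scale at 24 and 48 hours post-cesarean". So each patient contributes two primary measurements.

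Statistical Methods, item 1, fits a mixed linear model, "introducing the type of analgesia (TRON vs EPI) and the covariables considered in the model as fixed effects, with the patient as a random effect". It then itemises the covariables: newborn weight, breastfeeding, duration of the operation, previous caesarean, urgency category and extended surgery. Time of measurement is not among them, and no interaction is listed.

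The margin appears only under Sample Size and Power Calculations: "The minimum clinically important difference (MCID) of QoR-15 is 8 points, so we used it as the equivalence threshold". The same section concludes that "312 patients are needed to conduct this non-inferiority study of tramadol-ondansetron perfusion with an alpha error of 0.05 and a statistical power of 0.8". Statistical Methods does not mention the 8 points; its only criterion is a p-value below 0.05.

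Item 2 (Sequential VAS) describes the outcome as "Scale from 0-10 repeated every 4 hours" and says: "It will also employ a mixed linear regression model, introducing the same covariables as mentioned in the previous section". Measurement occasion is therefore not listed there either.

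**The concern.** A non-inferiority conclusion needs one stated quantity to hold against the margin. Here the endpoint names two times, the objective speaks of global recovery, and the listed model yields one analgesia coefficient. A reader could take the deciding quantity to be the 24-h difference, the 48-h difference, both, either, or their average. These rules have different power and different error rates, and the choice should not remain open once data are seen.

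There are two further consequences if both scores enter one model. Without an analgesia-by-time term, neither time named in the endpoint can be reported separately. Without a time term, the group means mix 24-h and 48-h scores in proportions that depend on how many 48-h scores are missing, so unequal loss moves the estimate whenever mean scores change between the two times.

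**Working it through.** **Inputs from the SAP.** Margin 8, SD 28.4, 312 patients, alpha 0.05, power 0.8. **Inferred, not stated:** 1:1 groups (156 each), true difference 0, one-sided 0.05. **Assumed, with ranges:** within-patient correlation r between the two scores of 0.3–0.9, the rise in mean score from 24 to 48 h, and the 48-h loss rates.

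**1. The plan's own figure.** n per group = 2 × 28.4² × (1.645 + 0.842)² / 8² = 155.8, so 156 per group and 312 in total. It reproduces, and it is sized for one comparison of two means. One-sided 0.025 would give 396 and a two-sided equivalence test 432, so neither is what was used.

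**2. One time point.** SE = 28.4 × √(2/156) = 3.216; power = Φ(8/3.216 − 1.645) = 0.80.

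**3. Equally weighted average of the two times.** With complete data, SE = 3.216 × √((1+r)/2). With a fraction l of 48-h scores lost in each group, and time and analgesia × time in the model, the variance of a group's average is 28.4²/(4 × 156) × (1 + r² + (1−r²)/(1−l) + 2r). Power = Φ(8/SE − 1.645). The last two columns use complete data, first with groups of 208 and 104, then with 1.96 in place of 1.645.

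| r | SE, complete | Power | SE, l = 0.2 | Power | Power, 2:1 | Power, one-sided 0.025 |
|---|---|---|---|---|---|---|
| 0.3 | 2.593 | 0.925 | 2.704 | 0.906 | 0.897 | 0.870 |
| 0.5 | 2.785 | 0.890 | 2.871 | 0.873 | 0.856 | 0.819 |
| 0.7 | 2.965 | 0.854 | 3.020 | 0.842 | 0.816 | 0.770 |
| 0.9 | 3.134 | 0.818 | 3.154 | 0.814 | 0.777 | 0.723 |

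**4. Bias from leaving time out.** Suppose scores rise by an amount R and a fraction l of a group has no 48-h score. The generalised-least-squares group mean then exceeds the 24-h mean by R × ((1−l)/(1+r)) / (2(1−l)/(1+r) + l). For r = 0.5 and R = 10 this is 4.615 at l = 0.10, 4.416 at 0.15 and 3.784 at 0.30. The group with more loss is therefore understated by 0.20 (15% versus 10%) or 0.83 (30% versus 10%). Over r = 0.3–0.9 the ranges are 0.18–0.24 and 0.75–0.97. Maximum-likelihood fits to 20,000 simulated patients per group gave 0.17–0.22 and 0.72–0.88. With equal loss and a constant true effect the bias is zero. If scores fall, the direction reverses.

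**5. Why the interaction is needed as well.** A time main effect alone removes the bias in step 4. But if the true difference is −8 at 24 h and 0 at 48 h, with 20% loss in both groups, that model's coefficient weights 24 h more heavily and lies 0.56–0.77 points below the equally weighted average of −4.

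**6. What an average can hide.** For the same −8 and 0, the average contrast declares non-inferiority with probability Φ(4/SE − 1.645) = 0.459, 0.417, 0.384, 0.356 for r = 0.3, 0.5, 0.7, 0.9. A 24-h contrast does so with probability 0.05.

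**7. Other rules, none of them adopted in the SAP (bivariate normal).** With 20% loss, the variance of a group's 48-h mean is (28.4²/156) × (r² + (1−r²)/(1−l)).

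| Rule | Complete data, r = 0.3 to 0.9 | 20% loss at 48 h |
|---|---|---|
| Power, 48 h alone | 0.80 | 0.73 to 0.78 |
| Power, both times required | 0.67 to 0.75 | 0.61 to 0.74 |
| Type I error, either time, unadjusted | 9.3% to 6.8% | not computed |

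**The case against.** The strongest reply is that this is close to a gap in wording. The model has one analgesia coefficient and the objective is global recovery, so the pooled effect is the natural contrast. With complete data it is unbiased for the average and holds its 5% error rate, and the trial is large enough for it. That is largely right, and it is why the point is an inexpensive improvement and not a fault that undermines the trial. What survives is that the SAP never says so, does not link that coefficient to the 8 points, and lists a model that cannot show either time.

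The bias can also fairly be called hypothetical. The SAP gives no rise and no loss rates, and under mild imbalance the shift is 2–3% of the margin (0.18/8 to 0.24/8).

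The one-model reading is itself likely but not certain. The patient random effect points to it, yet the single 90-day outcome is also given "A Mixed logistic regression model introducing the same covariables as mentioned in the previous section", so the word mixed does not settle how the two QoR-15 scores enter.

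Three stronger inferences should be resisted:
- **That the primary test has a type I error of 7–9%.** This would follow only from an unadjusted either-time claim, which the SAP does not make.
- **That 312 patients are too few.** The figure reproduces, and under its inferred assumptions it serves the average well.
- **That leaving out time biases the result as such.** It does so only when mean scores change between times and loss is unequal.

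**Conclusion.** The point holds as a specification gap in the primary analysis: there is no time or analgesia-by-time term for a two-time endpoint, and no named contrast for the margin. The potential bias is about 0.2 points under mild unequal loss and 0.7–1.0 points at 30% versus 10%, given an assumed 10-point rise, and it runs against the group losing more. It is nil with complete data, or with equal loss and a constant effect.

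Power for the average is 0.93–0.82 with complete data and 0.91–0.81 with 20% loss in each group. That rests on 1:1 groups, a true difference of 0 and one-sided 0.05. Group sizes are not fixed by design in this observational study. With 2:1 groups power falls below 0.80 at correlation 0.9, and with one-sided 0.025 it does so at correlation 0.7 or more.

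**What to change.** 1. Add categorical time (24 h, 48 h) and analgesia × time to the QoR-15 model.
2. State before analysis which contrast is tested against 8 points. The choice is the sponsor's. The equally weighted average of the 24-h and 48-h differences is closest to the present model and to the stated objective.
3. If the average is chosen, report the adjusted difference with its confidence interval at each time, so that a shortfall at one of them is visible.
4. If non-inferiority is instead required at both times, state the lower power given in the working.
5. Exclude an unadjusted either-time claim.
6. Add measurement occasion as a fixed effect in the VAS model.

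The cost is two parameters and one sentence for QoR-15, with no new data. The time-specific differences are less precise than the average: with complete data the 90% interval half-width is 1.645 × 3.216 = 5.3 points at one time, against 4.3–5.2 for the average. For VAS, categorical occasion adds about 11–12 parameters (12 occasions from 4 to 48 h, or 13 with 0 h). None of this corrects for loss that depends on the unseen 48-h score itself.

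### Adverse effects and rescue are called both a count and a yes/no under a Poisson model without robust variance, and the single 90-day chronic pain outcome gets a mixed logistic model whose patient variance the data cannot estimate

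*SAP*

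**What the plan says.** Statistical Methods items 4 (Adverse Effects) and 5 (Rescue Medication) carry the same instruction: "Count of events as yes/no. A mixed Poisson regression model introducing the same covariables as mentioned in the previous section". Neither item names a robust variance or a rule for counting events per woman. The matching objective is to "Compare the incidence of adverse effects between TRON and AL-EPI", and the endpoint is "Adverse effects within 48 hours post-cesarean", a single window. Rescue medication has no objective or endpoint of its own; Statistical Methods refers only to the need for it.

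Item 6 (Chronic Pain at 90 Days) prescribes: "A Mixed logistic regression model introducing the same covariables as mentioned in the previous section". The Endpoints section makes this an incidence at 90 days on the Numerical Rating Scale, and Data Collection and Management lists one contact after 48 hours, at 90 days.

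The only random effect named in the SAP is in item 1 (QoR-15), "with the patient as a random effect". No centre or other grouping appears.

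**The concern.** There are two separate problems.

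**Items 4 and 5.** A count and a yes/no are different outcomes and need different models. Incidence over one 48-hour window suggests one yes/no per woman for adverse effects; for rescue, only the reference to need points that way. On that reading a Poisson likelihood takes the variance to be p when it is p(1−p). Model-based intervals are then too wide, and a real difference in adverse effects or rescue, in either direction, is harder to detect. A patient random effect cannot repair this: it can only add variance, and a 0/1 outcome already varies less than Poisson assumes.

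**Item 6.** A patient random effect needs repeated measurements on the patient. With one binary value per woman, a larger patient variance combined with a larger treatment coefficient reproduces the same observed proportions. The reported odds ratio would then depend on where the software's variance estimate happens to land.

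**Working it through.** **Inputs.** N = 312 (SAP, Sample Size and Power Calculations) and significance at p < 0.05 (Statistical Methods), taken here as two-sided. The SAP gives no event risks and no group split, so all risks, the equal split of 156/156 and the 2:1 split are assumptions.

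**The plan's own figure.** With margin 8, SD 28.4, one-sided α 0.05 and power 0.80, n per group = 2 × 28.4² × (1.645 + 0.842)² / 8² = 155.8, rounded up to 156. The total is 312, so the stated figure reproduces. It serves here only to set the group size.

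**Items 4 and 5, one yes/no per woman.** Under equal risks p, the variance of the log risk ratio is 2(1−p)/(np); Poisson uses 2/(np). The SE ratio is 1/√(1−p), and the real two-sided α is 2[1 − Φ(1.96 × ratio)].

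| Assumed risk p | SE ratio | Real α |
|---|---|---|
| 0.05 | 1.03 | 0.044 |
| 0.10 | 1.05 | 0.039 |
| 0.20 | 1.12 | 0.028 |
| 0.30 | 1.20 | 0.019 |
| 0.50 | 1.41 | 0.006 |

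A simulation with two covariates (2000 replicates per risk) gave a type I error at p = 0.30 of 0.022 with model-based variance and 0.054 with robust variance.

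For power, SE_bin = √[(1−p₀)/(n₀p₀) + (1−p₁)/(n₁p₁)] and SE_Pois = √[1/(n₀p₀) + 1/(n₁p₁)]. Power with the correct variance is Φ[(log RR − 1.96 SE_bin)/SE_bin]. Power as planned is Φ[(log RR − 1.96 SE_Pois)/SE_bin].

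| Risks | Split (lower/higher risk) | SE_bin | SE_Pois | Correct variance | As planned |
|---|---|---|---|---|---|
| 10% vs 20% | 156/156 | 0.289 | 0.310 | 67% | 62% |
| 30% vs 45% | 156/156 | 0.151 | 0.189 | 77% | 59% |
| 30% vs 45% | 208/104 | 0.152 | 0.193 | 76% | 57% |
| 30% vs 45% | 104/208 | 0.168 | 0.207 | 67% | 50% |

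The patient effect does not help. For 47 vs 70 events of 156, the Poisson-normal log-likelihood is −229.5, −235.2, −251.3 and −292.3 at patient SD of about 0, 0.5, 1 and 2, so the estimate goes to zero.

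**Items 4 and 5, several yes/no records per woman.** For k records with within-woman correlation r, and leaving out the random effect, the ratio becomes 1/√[(1−p)(1+(k−1)r)]. With k = 2 and p = 0.30 it is 1.20 at r = 0 and 1.05 at r = 0.3. The excess is gone once r ≥ p/[(1−p)(k−1)]. For k = 6 that is r ≥ 0.02 at p = 0.10 and r ≥ 0.09 at p = 0.30.

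**Item 6, treatment only.** Assume 10% vs 15% with 156 per group. For each patient SD, the group intercepts are solved by Gauss-Hermite quadrature so that the marginal risks are 0.10 and 0.15.

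| Patient SD | OR (95% CI) | Log-likelihood |
|---|---|---|
| 0 | 1.59 (0.80–3.15) | −116.66 |
| 1 | 1.68 (0.78–3.59) | −116.66 |
| 2 | 1.95 (0.73–5.18) | −116.66 |
| 3 | 2.37 (0.67–8.39) | −116.66 |

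The fit is identical in every row, and z is 1.33 throughout.

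**Item 6, with covariates.** Covariates of the listed types identify the variance only through the assumed link shape. In 200 simulated datasets (n = 312, treatment plus seven covariate terms with assumed effects, true patient SD 0), the log-likelihoods over SD 0 to 3 differed by a median of 0.10 and at most 0.74. Excluding a value at the 95% level needs 1.92. The best-fitting SD was 0 in 90 datasets and 3, the edge of the grid, in 106. The median OR moved from 1.65 at SD 0 to 2.48 at SD 3, while Wald z changed by a median of 0.05. A second simulation, set up separately and also with assumed effects, gave a median spread of 0.16, a maximum of 0.90 and a median OR moving from 1.66 to 2.53.

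**The case against.** On items 4 and 5, the wording can be read as several yes/no records per woman, by type of effect or by interval, added up. Counting, Poisson and a mixed model all fit that reading, and the study does collect data at 24 and 48 hours. With many correlated records the excess in the standard error vanishes, and a patient effect is then needed. This stands as a possible reading, but the SAP does not state it. It turns the point into an ambiguity that must be settled, not proof that the model is wrong. It is also true that the point estimate is unbiased, the error is conservative, no non-inferiority claim is attached to adverse effects, and at risks of 5–10% the standard error is only 3–5% too large.

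On item 6, the item itself does not name the patient as the random effect. That is carried over from item 1, but no other grouping is available. The test result hardly changes. In 90 of 200 simulated datasets the best fit was SD 0, which is ordinary logistic regression. The upper end of the odds-ratio range reflects where the SD grid stopped, and odds ratios at larger SD are patient-specific, so part of the movement is a change of target. These points limit the consequence to the reported estimate and its interval. They do not justify a variance the data cannot inform.

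**Conclusion.** The concern holds, most firmly for item 6. With one chronic pain value per woman and the patient as the only named random effect, the odds ratio is set by a variance on which the data are almost silent: 1.59 to 2.37 for SD 0 to 3 at assumed risks of 10% vs 15%, with practically the same test statistic.

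For items 4 and 5 the outcome form is contradictory as written. If it is one yes/no per woman, the loss runs from negligible at low risks to 17–19 percentage points of power in the 30% vs 45% examples. If it is a true count or many correlated records, the planned mixed Poisson model can be adequate and only the wording is wrong. All event risks and group splits are assumptions.

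These are not primary outcomes: the QoR-15 model and N = 312 are unaffected. The plan should be corrected before analysis, but the point does not threaten the main conclusion.

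**What to change.** - **Items 4 and 5:** state for each outcome whether it is one yes/no per woman, several yes/no records per woman, or a number of events.
  - One yes/no per woman: use logistic regression, or Poisson regression with robust standard errors if risk ratios are wanted, without a patient random effect.
  - Several yes/no records per woman: say what the records are, and keep the patient random effect.
  - Number of events: delete the yes/no wording and keep a count model that allows overdispersion, which the planned mixed Poisson does.
- **Item 6:** use ordinary logistic regression with type of analgesia and the listed covariates.
- **General rule:** use a patient random effect only where a woman has repeated measurements.

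The cost is a change of SAP wording and about one line of code per model. No new data are needed.

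### The 90-day chronic-pain model puts eight slopes on one yes/no outcome per woman with no method for sparse events; Firth penalisation is a cheap safeguard

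*SAP*

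**What the plan says.** Item 6 of Statistical Methods in the SAP gives the whole analysis of 90-day chronic pain in one sentence: "A Mixed logistic regression model introducing the same covariables as mentioned in the previous section". The list it points to is the one under item 1 (QoR-15): newborn weight, breastfeeding, duration of the intervention, previous caesarean, a three-level urgency factor, and "Extended surgery: tubal sterilization or any other deviation from a standard caesarean section".

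The sample size section supports QoR-15 only: "The minimum clinically important difference (MCID) of QoR-15 is 8 points, so we used it as the equivalence threshold", "with a standard deviation of 28.4", and from these "we calculated that 312 patients are needed to conduct this non-inferiority study" "with an alpha error of 0.05 and a statistical power of 0.8". The SAP gives no expected incidence of chronic pain, no NRS cut-off for a case, no allowance for loss by day 90, and no penalised, exact or reduced model if events are few.

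The section on randomisation and blinding states: "This study does not involve randomization as it is observational". The listed covariables are therefore the only control of confounding that the SAP names.

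**The concern.** The covariable list was written for a continuous score read twice per woman. A binary outcome read once carries far less information, and what matters is the number of events, not the number of women. When a category holds no events, or only events, the maximum-likelihood estimate of its coefficient does not exist. Software then reports non-convergence or a very large coefficient with a meaningless standard error.

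Chronic-pain incidence is a stated secondary objective. If the planned fit fails, the obvious response is to drop or merge covariables once the data are known. In a non-randomised comparison that changes the confounding adjustment after the fact. A second, smaller effect is that maximum likelihood with few events per slope pushes a non-null odds ratio away from 1.

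**Working it through.** **The plan's own figure.** With margin 8, SD 28.4, true difference 0, power 0.8, equal groups (assumed) and one-sided alpha 0.05 (the SAP does not state sidedness):

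n per group = 2 × (1.645 + 0.842)² × 28.4² / 8² ≈ 155.8, rounded up to 156, so 312 in total. This reproduces the SAP. The chronic-pain outcome plays no part in it.

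**Slopes.** Analgesia 1 + newborn weight 1 + breastfeeding 1 + duration 1 + previous caesarean 1 + urgency 2 (three levels) + extended surgery 1 = 8.

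**Events.** Events = 312 × incidence; events per slope = events / 8. Incidence is assumed, since the SAP gives none.

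| Assumed incidence | Events | Per slope |
|---|---|---|
| 5% | 15.6 | 1.95 |
| 10% | 31.2 | 3.9 |
| 15% | 46.8 | 5.9 |
| 20% | 62.4 | 7.8 |
| 30% | 93.6 | 11.7 |

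The common rule of thumb of ten events per slope would need 80 events, an incidence of 80/312 = 25.6%. With an assumed 20% loss by day 90 (312 × 0.8 ≈ 250 women), 5–15% gives about 12–37 events, or 1.6–4.7 per slope.

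**Simulation.** Eight-slope logistic model, 312 women, equal groups, no patient random effect, 1,500 data sets per setting, modest covariable effects. Other assumed prevalences were 20% previous caesarean and 80–85% breastfeeding. A coefficient counts as diverged if the fit fails or a slope exceeds 8 in absolute value.

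Share of data sets with any diverged coefficient, true odds ratio 2:

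| Emergency / extended surgery (assumed) | about 16 events | about 31 | about 47 |
|---|---|---|---|
| 20% / 20% | 9% | not run | not run |
| 10% / 8% | 32% | 7% | 1% |
| 10% / 6% | 38% | 7% | 2% |
| 4% / 4% | 68% | not run | 17% |

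In a separate set of runs, losing 20% of the women raised these shares from 43%, 11% and 3% to 55%, 19% and 7%.

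**The TRON coefficient.** It diverged in under 1% of data sets in every tabulated setting where it was counted separately, and in at most 1.6% in any run. Its mean log odds ratio at a true value of 0.693, with 10% / 8% categories, was:

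- about 16 events: 0.792, 14% too large (geometric mean odds ratio 2.21; Firth 2.03);
- about 31 events: 0.732, 5.5% too large (2.08; Firth 1.98);
- about 47 events: 0.727, 5% too large (2.07; Firth 2.00).

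Over all settings the excess was about 3–9% at 31–47 events and about 8–14% at 16. One run at 16 events with 4% categories gave 6% (odds ratio 2.08; Firth 1.92). That is within simulation error of the range: 0.67/√1500 ≈ 0.017, or 0.017/0.693 ≈ 2.5 percentage points. At a true odds ratio of 1 the mean was 0.99–1.01. Coverage of Wald 95% intervals was 95–97% in fits that did not diverge.

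**Precision.** Root-mean-square error of the TRON log odds ratio with 10% / 6% categories, maximum likelihood against Firth:

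- 5% incidence: 0.67 against 0.57 (0.10/0.67 = 15% lower);
- 10%: 0.44 against 0.41 (7% lower);
- 15%: 0.36 against 0.34 (6% lower);
- 20%: 0.310 against 0.296 (5% lower).

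Firth also had the lower error in all 24 settings of a further simulation covering 5–25% incidence, true odds ratios 1 and 2, and three sets of category prevalences.

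**The case against.** The strongest reply is that the SAP fixes neither the event rate nor the category sizes. Chronic pain is to be studied through NRS results and medication use, so a case may be defined broadly. Excluding women with prior pain makes a low rate plausible but sets no figure. At 25–30% incidence the concern largely goes. This stands: 16–47 events is an assumption, and the divergence rates move widely with assumed prevalences.

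A reader might infer that separation makes the TRON odds ratio infinite or seriously overstated. That does not follow. Divergence falls on small covariable categories, not on the treatment term. The treatment bias is nil at the null, modest otherwise, and well below the sampling error of the estimate.

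It can also be said that item 6 asks for a mixed model and names no estimator, whereas the simulation fits an ordinary logistic model by maximum likelihood. That is correct. The only random effect the SAP names is the patient, and a patient effect cannot be estimated from one yes/no outcome per woman. This is a separate fault; removing the effect leaves the sparsity described here.

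Finally, Firth might be called a matter of taste for a secondary outcome. Against that, its error was lower in every setting tried, and stating it beforehand removes a choice that would otherwise be made with the data in view.

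**Conclusion.** The point holds as a cheap improvement, not as a serious error. Item 6 commits eight slopes to a once-measured binary outcome and says nothing about sparse events.

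Assuming 5–15% incidence and 4–20% prevalence for each of emergency and extended surgery, some covariable coefficient diverges in about 10–70% of data sets at 16 events and 0–20% at 47. The practical harm is failed fits, covariable estimates that cannot be reported, pressure to alter the adjustment set in a non-randomised study, and some loss of precision on TRON.

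The documents do not support a claim that the TRON odds ratio will be badly exaggerated, nor that 16–47 events is the expected number. With no loss to follow-up assumed, 312 evaluable women is a favourable case.

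**What to change.** In item 6, replace the mixed logistic model with a Firth penalised logistic regression, one row per woman, containing type of analgesia and all six listed covariables. State profile-penalised-likelihood confidence intervals. Because the objective concerns incidence, also report the adjusted risk in each group, computed after the usual intercept correction, beside the odds ratio. Change the estimator only and leave the covariable list as it is.

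The cost is a line or two of SAP text and a standard software option. The drawback is slight shrinkage of estimates and, without the intercept correction, of predicted risks. If incidence turns out at 20–25% or more, little is gained and almost nothing is lost.
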